#### **DIRECTIONS FOR USING THE ACT-O-VIAL SYSTEM**

1. Press down on plastic activator to force diluent into the lower compartment.
2. Gently agitate to effect solution.
3. Remove plastic tab covering center of stopper.
4. Sterilize top of stopper with a suitable germicide.
5. Insert needle squarely through center of stopper until tip is just visible. Invert vial and withdraw dose.

**Further dilution is not necessary for intravenous or intramuscular injection. For intravenous infusion,** first prepare solution as just described. **The 100 mg** solution may then be added to 100 to 1000 mL of 5% dextrose in water (or isotonic saline solution or 5% dextrose in isotonic saline solution if patient is not on sodium restriction). **The 250 mg** solution may be added to 250 to 1000 mL, the **500 mg** solution may be added to 500 to 1000 mL and the **1000 mg** solution to 1000 mL of the same diluents. In cases where administration of a small volume of fluid is desirable, 100 mg to

### Interval Bolus Delivery of Cortisol in Children with CAH

3000 mg of SOLU-CORTEF may be added to 50 mL of the above diluents. The resulting solutions are stable for at least 4 hours and may be administered either directly or by IV piggyback.

When reconstituted as directed, pH's of the solutions range from 7 to 8 and the tonicities are: 100 mg ACT-O-VIAL, .36 osmolar; 250 mg ACT-O-VIAL, 500 mg ACT-O-VIAL, and the 1000 mg ACT-O-VIAL, .57 osmolar. (Isotonic saline=.28 osmolar.)

#### **7.1.2 Dosage and Administration**

The parents of our children are already familiar with as the 100 mg ACT-O-VIAL as IM hydrocortisone injection is used at home in cases of acute stress or illness when the children are not able to take oral medication. Parents will be instructed to further dilute the solution with another 8 mL of 0.9% normal saline into the infusion syringe and visually inspect the hydrocortisone solution for particulate matter and discoloration.

The patients will receive their usual oral hydrocortisone dosing throughout and the first treatment period until the SQHC pump is initiated at admission 2. During admission 2, we will use each patient's total daily dose (TDD) of HC to determine the doses to be delivered during the 33-hr period. The infusion pump will be set to rapidly deliver a hydrocortisone pulse dose every 3 hr to attain an ultradian rhythm. The 24-hr schedule and percentage of the TDD of HC will be as follows: approximately 60% of the TDD of HC will be delivered in 3 equal pulses at 0300, 0600 and 0900. Another 35% will be delivered in 3 equal pulses at 1200, 1500 and 1800 and the remaining 5% at 2100 and 2400. After the 24-hr serum sample at 0600 the next morning, the pump will be disconnected and the subject will be sent home on their usual oral HC dosing regimen. If concentrations are outside acceptable ranges, the initial SQHC pump settings will be adjusted from the Admission 2 dosing as needed to attain acceptable concentration ranges. Individual pulse doses may be increased or decreased but the frequency of pulses will be fixed to every 3 hours. After determining appropriate SQHC pump settings, the subjects will return to clinic at week 9 to initiate the 6-week SQHC ambulatory pump therapy phase.

During the 6-week pump treatment, multiple cortisol, D4A and 17OHP concentrations will become available and they may suggest, along with clinical impressions, that the pump dosing setting needs to be revised. It is critical to note that subjects will not be required to stay on the initial bolus dosing schedule for 6 weeks. Rather, standard clinical practice will be used to guide SQHC pump dosing adjustments. Specifically, D4A and 17OHP concentrations will be evaluated along with clinical information provided by the patient that are indicative of hypocortisolism such as fatigue, nausea, diaphoresis, low blood pressure, dizziness or headache. This is currently the standard of care for pediatric CAH patients. Should incongruous information be observed, clinical impressions take precedence along with D4A concentrations, and then 17OHP concentration. Cortisol concentrations are not generally part of routine patient care and will play a lesser role in dosing changes. The changes in dose settings may involve increasing or decreasing the HC TDD, or perhaps changing the percentage of TDD administered at a given time, but the 3-hr dosing intervals will remain fixed.

Every 72 hours, the family will be instructed to replace the hydrocortisone infusion syringe and solution, and the site of subcutaneous infusion will be changed.

Parents will be instructed to visually inspect the parenteral hydrocortisone solution for particulate matter and discoloration prior to administration into the pump cassette. Parents are already familiar with this process as IM hydrocortisone injection is used at home in cases of acute stress or illness when the children are not able to take oral medication.

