#### **5.2.2 Exclusion Criteria**

- Patients with non-classic CAH.
- Patients on:
  - Dexamethasone
  - Prednisone, or
  - inhaled steroids.
- Patients with total daily dose of HC dosing regimen (min 10 mg) that cannot meet the required smallest volume to be delivered by the pump (0.2 mg)
- Non-English speaking patients

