#### **6.2.1.4 Week 7 (SQHC Pump 33 hours)**

At week 7, subjects will be re-admitted for Crono P subcutaneous HC (SQHC) infusion pump training in which the device will be used for 33 hrs and include a 24-hr PKPD study while on the SQHC pump. Training will emphasize proper aseptic catheter placement, care of the insertion site, reconstituting the solution and filling the infusion syringe. HC sodium succinate (SOLU-CORTEF) sterile powder will be used for the SQHC pump as it is FDA approved for intramuscular and intravenous routes for CAH and Addison's disease. HC sodium succinate comes in a two-compartment vial (Act-O-Vial) containing a 100 mg dose in the lower compartment and 2 ml sterile water in the upper compartment (100 mg/2 ml). Parents will be instructed to further dilute the solution with another 8 ml of 0.9% normal saline into the infusion syringe, for a final concentration of 100 mg/10 ml (10 mg/ml). Parents will be trained to visually inspect the HC sodium succinate solution for particulate matter and discoloration. The parents of the children seen at the CAH Center are already familiar with the 100 mg Act-O-Vial as the IM HC sodium succinate injection is used at home in cases of acute stress or illness when the children are not able to take oral medication.

Subjects will have a physical exam. Pump therapy during this admission will begin at 9 pm and continue for 33 hours. We will use each patient's total daily dose (TDD) of HC to determine the doses to be delivered during the 33-hr period. The 24-hr schedule and percentage of the TDD of HC will be as follows: approximately 60% of the TDD of HC will be delivered in 3 equal pulses at 0300, 0600 and 0900. Another 35% will be delivered in 3 equal pulses at 1200, 1500 and 1800 and the remaining 5% at 2100 and 2400. Following delivery of the 9:00 pm, 12:00 am, and 3:00 am pulses, a 24-hr PKPD study will be initiated at the 6:00 am pulse using the same sampling schedule of cortisol, 17OHP, ACTH and D4A as the first admission. Urine collection will proceed as the first admission beginning at 0600. Saliva samples will be collected at the same time points as in admission 1 (0600, 0700, 1200, 1300, 1800, and 1900) irrespective of dosing. Salivary samples will be sent to Quest Diagnostics for adrenal steroid measurements through LC-MS/MS assay.

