#### **6.2.2 Weeks 9-14 (SQHC Pump)**

### **6.2.2.1 Weeks 9-13**

Week 9 (outpatient visit) The patient will meet [name] and the study nurse coordinator at Nucleus (Prism) for initiating the 6-wk SQHC pump phase. The patient will have a physical exam and the nurse coordinator will review the patient's recorded daily blood pressure, subject diary, adverse events and any medications taken. It is our standard policy to make sure that families have parenteral hydrocortisone to use during emergencies. We will instruct the patients to call [name] before administering any parenteral dose during this phase. After the first four supervised home visits by the nurse coordinator, the family, as instructed will replace the HC infusion syringe and solution, and the site of SQ infusion every 72 hours. As with insulin, we recognize that there may be variability in drug absorption associated with different sites of SQ injection pump infusion therapy. Each subject will be evaluated for appropriate site for SQ infusion (i.e. gluteal area, abdominal area).. Parents will be instructed to visually inspect the parenteral HC solution for particulate matter and discoloration prior to administration into the pump.

After the outpatient visit, during week 9, the subject/family will be called on the days that the RN coordinator is not completing home visits. This call is the review pump use, adverse events and other questions or concerns.

Weeks 9-13: The nurse coordinator will visit subjects at home seven times for safety monitoring, which includes a nursing assessment, and measurement of cortisol, 17OHP, ACTH and D4A concentrations during the SQHC pump period. During the home visits, along with the blood draws, saliva will be collected and measured through VerOFy® cortisol (VCORT) with the remaining salivary sample sent to Quest Diagnostics for free cortisol measurements through LC-MS/MS assay. VCORT is IDE exempt per the requirements outlined in 21CFR812.2(c) and in 21CFR809.10(c). The nurse coordinator will complete their assessment and review the patient's recorded daily blood pressure, subject diary, adverse events and any medications taken. At Visit 13, an Actigraph Link accelerometer will be provided for monitoring daily activity and sleep patterns for one week.

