### **7.1.3 Dosage adjustments**

The following dosage adjustments may be made during the course of the study in the event of intercurrent illness, pump failure or symptoms of adrenal insufficiency occur.

- For fever > 101 degrees F: add oral hydrocortisone to the patient's regimen, which will be double the amount of the daily dose that the patient receives through the SQ pump. The additional oral stress hydrocortisone dose will be divided in 4 equal doses every 6 hours. The subject's family will be instructed to administer an antipyretic (Tylenol, ibuprofen, etc).
- For a serious physical injury or broken bone(s), administer a stress dose of hydrocortisone as described above.
- In the event of severe illness, trauma, or inability to tolerate oral hydrocortisone, unconsciousness, or repeated vomiting: 75 mg/m^2/day of Solucortef intramuscular injection will be administered immediately. The family will be instructed to seek Emergency Department care to initiate IV hydrocortisone and fluid replacement as they typically do as part of the standard therapy to prevent adrenal crisis.
- In the event of pump failure, patients will be instructed to resume their usual oral hydrocortisone dose until a replacement pump is given to the family.
- In the event of an occlusion that results in missed hydrocortisone dosing, patients will be instructed to change the infusion set and notify the investigators. If occlusion persists, patients will be instructed to resume their usual oral hydrocortisone dose until occlusion is resolved.
- A pump malfunction that results in delivery of the entire reservoir (worst case scenario 100 mg of hydrocortisone) is not a life threatening event as children receive similar or greater amounts of hydrocortisone during illness. If the entire reservoir is delivered, patients will be instructed to notify the investigators and return to their usual oral hydrocortisone dosing until a replacement pump is given to the family.

At all times the PI will be available to the families. If pump therapy is stopped at any point the investigator will evaluate the participant and re-initiate the pump treatment when deemed clinically appropriate. Once the pump is resumed, pump treatment will be continued in order to meet the total 6 weeks of pump treatment.

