### **7.3.2 Storage**

Store unreconstituted product at controlled room temperature 20° to 25(C(68° to 77( F). Store solution at controlled room temperature 20° to 25(C (68° to 77( F) and protect from light. Use solution only if it is clear. Unused solution should be discarded after 3 days.

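### One 100 mg fill changed every 72 hours supplies at most 33.3 mg/day; the plan neither states this nor checks programmed doses against it

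*Combined protocol and SAP*

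**What the plan says.** Section 6.2.1.4 has parents dilute a 100 mg vial "for a final concentration of 100 mg/10 ml (10 mg/ml"). Section 7.1.2 repeats the step: "further dilute the solution with another 8 mL of 0.9% normal saline into the infusion syringe". Section 7.1.3 confirms the content of a full syringe when it describes "delivery of the entire reservoir (worst case scenario 100 mg of hydrocortisone").

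The change interval appears twice. Section 7.1.2 has "Every 72 hours, the family will be instructed to replace the hydrocortisone infusion syringe and solution", and section 6.2.2.1 has families "replace the HC infusion syringe and solution, and the site of SQ infusion every 72 hours". Section 7.3.2 adds "Unused solution should be discarded after 3 days".

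Pump doses start from each child's own total daily dose (TDD; sections 4, 6.2.1.4 and 7.1.2). During the six weeks, "The changes in dose settings may involve increasing or decreasing the HC TDD"; section 7.1.2 also lets single pulses go up or down after admission 2. Neither statement refers to what the fill can supply.

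The only eligibility rule on pump capacity is in section 5.2.2: "Patients with total daily dose of HC dosing regimen (min 10 mg) that cannot meet the required smallest volume". That is a lower bound. Ages run to 18 (section 5.2.1), and the current criteria contain no body surface area limit.

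**The concern.** A fixed fill and a fixed change interval together imply a maximum daily dose. The plan gives both but does not draw the consequence, and it places no check at the upper end.

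Above that maximum, a family following the 72-hour rule exactly would have an empty syringe before the change. These children depend on the drug, and section 2 gives a median half-life of 58 minutes, so missed pulses mean low cortisol. That is first a safety matter.

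It also bears on interpretation. If the shortfall fell within the admission 3 profile, it would count as pump-period hypocortisolemia in the primary outcome (sections 3.1 and 11.1), although its cause would be supply and not the pattern of delivery. Low-cortisol symptoms or a raised androstenedione could also prompt a further increase under section 7.1.2, which would empty the fill sooner. Section 4 times the home visits of the first two weeks, with their blood draws, at site changes, which is where a shortfall would fall.

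**Working it through.** **Inputs.** Vial 100 mg in 2 mL plus 8 mL saline (section 6.2.1.4). Change every 72 h, or 3 days (sections 6.2.2.1 and 7.1.2). Schedule: about 60% of TDD in three equal pulses at 0300, 0600 and 0900; 35% in three equal pulses at 1200, 1500 and 1800; 5% at 2100 and 2400 (section 7.1.2). I took the 5% as 2.5% per pulse, which the plan does not state. Cited dose range 10-15 mg/m²/day (section 2).

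**The plan's own figure.** 100 mg / (2 + 8) mL = 10 mg/mL, as stated.

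**Supply limit.** 60% + 35% + 5% = 100% of TDD per 24 h. Any 72-hour window holds 24 pulses, which is 3 × TDD whatever the hour at which the fill starts. Setting 3 × TDD = 100 mg gives TDD = 33.3 mg/day.

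**Priming or residual loss.** No volume is given. As an assumption, losses of 0.25 to 1 mL would give (100 − 2.5)/3 = 32.5 down to (100 − 10)/3 = 30.0 mg/day.

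**Shortfall per 72-hour cycle.** The timing comes from stepping through the pulses for each of the eight possible first pulses, with no priming loss.

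| TDD (mg/day) | Needed in 72 h (mg) | Undelivered (mg) | First pulse not fully delivered |
|---|---|---|---|
| 30 | 90 | 0 | none |
| 34 | 102 | 2 | 63-69 h |
| 35 | 105 | 5 | 63-69 h |
| 40 | 120 | 20 | 54-63 h |
| 50 | 150 | 50 | 48 h |

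**Example at 40 mg/day, first pulse at 1200.** The three morning pulses are 0.20 × 40 = 8 mg each. Before the last three, 120 − 24 = 96 mg has been used and 4 mg remains. The 0300 pulse (63 h) is halved and the 0600 and 0900 pulses are missed: 4 + 8 + 8 = 20 mg. Section 2 places the ACTH peak at about 0600.

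**Who could reach the limit.**
- At 15 mg/m²/day: 33.3/15 = 2.22 m². At 10 mg/m²/day: 33.3/10 = 3.33 m².
- Above the cited range, for illustration only, 20 mg/m²/day: 33.3/20 = 1.67 m².
- By dose increase: 33.3/30 − 1 = 11% from 30 mg/day; 33.3/25 − 1 = 33% from 25 mg/day.

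**Context from the revision history.** At the superseded upper surface area limit of 2.04 m², 15 × 2.04 = 30.6 mg/day and 3 × 30.6 = 91.8 mg, which fits in the fill. That limit kept the cited dose range within supply. The logged reason for its removal discusses only reaching a minimum volume.

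**The case against.** No stated figure is wrong: the concentration reproduces, and the limit matters only if a child passes it. The documents give no distribution of daily doses, and at most twelve children are enrolled. Within the cited range, only a very large adolescent would reach 33.3 mg/day before any increase. Fever dosing in section 7.1.3 is oral and does not draw on the syringe. All of this stands. A reader might infer that children in this trial will run out of drug; the documents do not show that.

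Nor do they support assuming that a run-out would go unnoticed. Only researchers set the pump (section 4), its display shows operations and diagnostics (section 8), families are trained on alarms (section 9.3), and week 9 has a call on days without a home visit. The device manual is not among the documents. These are real mitigations, but none names an empty reservoir. Section 7.1.3 covers pump failure, occlusion and accidental delivery of the whole reservoir, but not emptying in normal use. Inspection of syringe volume in section 9.3 follows a low blood pressure reading, so it comes after the event.

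The 72 hours can also be read as a maximum interval, in line with the 3-day solution life. Nothing forbids an earlier change, but nothing instructs one, and both statements of the interval are written as a fixed routine.

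Finally, it is tempting to divide 100 mg by the daily dose and quote 68.6 h of supply at 35 mg/day or 60.0 h at 40 mg/day. That assumes a constant rate, whereas the pump gives unequal pulses. The pulse-based ranges are the ones to use, and at 40 mg/day the first short pulse can come as early as 54 h.

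**Conclusion.** The point holds conditionally. One fill under the 72-hour rule supplies at most 33.3 mg/day, less any priming loss. No section states this, checks for it, or provides for a higher programmed dose. Above it, the last pulses of each cycle are not delivered: 5 mg per cycle at 35 mg/day and 20 mg at 40 mg/day.

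The limit rests only on the 100 mg fill, the 72-hour interval and a repeating daily schedule. The timing of the first short pulse also rests on the initial 60/35/5% split, and would shift if the percentages were changed. The number of children affected cannot be estimated and is probably small. The reasons to act are the consequence for a cortisol-dependent child and the possible contamination of the primary outcome.

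A reader might take 33.3 mg/day as a proper eligibility or dosing ceiling. The documents do not support that. The figure only describes what the present fill and interval can supply, and the conflict could be settled through the fill, the interval or the dose text.

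**What to change.** Reconcile sections 5.2.2, 6.2.1.4, 6.2.2.1, 7.1.2, 7.1.3 and 7.3.2 on the fill amount, the 72-hour change rule, the solution life, the one-sided capacity check and the permission to increase the dose. The result should be that, whenever pump settings are set or changed, the programmed 72-hour requirement (3 × TDD, plus any priming loss) is compared with the fill.

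How a requirement larger than the fill is handled is for the sponsor and investigator to decide. No dose limit or change interval is proposed here.

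The cost is a few sentences of protocol text and one multiplication at each setting. It needs no new data and does not change the analysis.

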### **7.1.3 Dosage adjustments**

The following dosage adjustments may be made during the course of the study in the event of intercurrent illness, pump failure or symptoms of adrenal insufficiency occur.

- For fever > 101 degrees F: add oral hydrocortisone to the patient's regimen, which will be double the amount of the daily dose that the patient receives through the SQ pump. The additional oral stress hydrocortisone dose will be divided in 4 equal doses every 6 hours. The subject's family will be instructed to administer an antipyretic (Tylenol, ibuprofen, etc).
- For a serious physical injury or broken bone(s), administer a stress dose of hydrocortisone as described above.
- In the event of severe illness, trauma, or inability to tolerate oral hydrocortisone, unconsciousness, or repeated vomiting: 75 mg/m^2/day of Solucortef intramuscular injection will be administered immediately. The family will be instructed to seek Emergency Department care to initiate IV hydrocortisone and fluid replacement as they typically do as part of the standard therapy to prevent adrenal crisis.
- In the event of pump failure, patients will be instructed to resume their usual oral hydrocortisone dose until a replacement pump is given to the family.
- In the event of an occlusion that results in missed hydrocortisone dosing, patients will be instructed to change the infusion set and notify the investigators. If occlusion persists, patients will be instructed to resume their usual oral hydrocortisone dose until occlusion is resolved.
- A pump malfunction that results in delivery of the entire reservoir (worst case scenario 100 mg of hydrocortisone) is not a life threatening event as children receive similar or greater amounts of hydrocortisone during illness. If the entire reservoir is delivered, patients will be instructed to notify the investigators and return to their usual oral hydrocortisone dosing until a replacement pump is given to the family.

At all times the PI will be available to the families. If pump therapy is stopped at any point the investigator will evaluate the participant and re-initiate the pump treatment when deemed clinically appropriate. Once the pump is resumed, pump treatment will be continued in order to meet the total 6 weeks of pump treatment.

## **7.2 Cortef® hydrocortisone tablets**

### **7.2.1 Description**

Cortef Tablets contain hydrocortisone which is a glucocorticoid. Glucocorticoids are adrenocortical steroids, both naturally occurring and synthetic, which are readily absorbed from the gastrointestinal tract. Hydrocortisone USP is white to practically white, odorless, crystalline powder with a melting point of about 215° C. It is very slightly soluble in water and in ether; sparingly soluble in acetone and in alcohol; slightly soluble in chloroform.

### **7.2.2 Dosage and Administration**

Patients will be receiving their usual dosing regimen of hydrocortisone tablets during the first treatment period.

## **7.3 Receiving, Storage, and Dispensing**

### **7.3.1 Receipt of Drug Supplies**

Upon receipt of the of the study treatment supplies, an inventory will be performed and a drug receipt log filled out and signed by the person accepting the shipment. The designated study staff will count and verify that the shipment contains all the items noted in the shipment inventory. Any damaged or unusable study drug in a given shipment (active drug or comparator) will be documented in the study files.

